2.6. Randomisation

Participants are randomised to either a) selfBACK DSS in addition to usual care or b) usual care only. The randomisation is performed as a block randomisation with permuted blocks of random size unknown to the research team and stratified by country and care provider (i.e. general practitioner, physiotherapist,

chiropractor, or Spine Centre). The allocation ratio between the SELFBACK DSS in addition to usual care and the usual care groups is 1:1. Randomisation will be performed by a web-based randomisation system (Web Case Report Form; WebCRF) developed and administered by Unit of Applied Clinical Research, Faculty of Medicine and Health Sciences, NTNU, Trondheim, Norway. This unit is not otherwise involved in the trial management or trial conduct. A contractual agreement has been signed with the Unit of Applied Clinical Research concerning their role and responsibilities in the project. The WebCRF system will hold a minimal data set on all screened participants (variables include: a trial id number, country, care provider, recruitment site, age, gender).

2.7. *Blinding*

The study is a single-blinded study. Participants are not blinded to group allocation. The analysis and interpretation of the study results will be performed by researchers blinded to group allocation. Once the study is completed, a copy of the data will be extracted in pseudonymised form for statistical analyses. All personal information that may lead back to specific participants (i.e. e-mail address, username etc.) will be removed from the data. The information concerning group allocation will be added to the dataset with the intervention and control group randomly labelled as A and B. The randomisation key (i.e. document entailing information on which group is which) is kept at the Unit of Applied Clinical Research at NTNU. They will provide the randomisation key to the research team once a blinded interpretation of the results is finalized (see section 5.2).

3. Interventions

3.1. *Usual care*

Participants randomised to usual care will follow any diagnostic or treatment-related pathway (e.g. receive information, advice or treatment) as instructed by their HCP. They are also allowed to seek care, treatment or help elsewhere as normal. After the completion of the trial at 9 months, participants who have completed all follow-up assessments are contacted and offered a wearable device similar to the SELFBACK intervention group.

3.2. *SELFBACK in addition to usual care*

The SELFBACK intervention is a digital DSS for self-management of LBP provided to the participant via a smartphone app (SELFBACK app) [26]. In addition, the participant is provided with a wearable device (i.e., a step-detecting wristband) that interacts with the SELFBACK app. Based on the step count and participant's self-reported data, the SELFBACK app provides individually tailored self-management plans including educational messages, physical activity advice and exercise recommendations matched to the participant's health status, as generated by the DSS. Importantly, the intervention is not intended to replace follow-up by HCPs, but to supplement the ordinary care by the HCP, and the participant is informed accordingly. Thus, participants randomised to the SELFBACK intervention may continue to seek care, treatment or help as normal.

Stakeholder and user involvement are increasingly seen as essential especially in the context of complex interventions. It is seen as important to enhance engagement, empowerment and to maximize long-term sustainability. User involvement has been a key feature during the development of the selfBACK system and the design of trial procedures. We have had direct input from patients through a range of mechanisms that are described elsewhere [26]. The content of the intervention was developed using

Intervention Mapping (IM). IM is a six-step process with each step consisting of several tasks, which, once completed, inform the next step, as detailed by Bartholomew et al. [28]. The IM process aims to facilitate participation and consultation from all relevant stakeholders. It provides a structure for the integration of theory, empirical findings from the literature, and information collected from the target population. In short, the first step of the IM process of this project consisted of a review of international clinical practice guidelines for management of LBP. The guidelines consistently endorse important elements such as education about LBP, and uptake of evidence-based self-management behaviours by participants; including physical activity and specific exercises as well as cognitive behavioural therapy (CBT) to promote self-management for people with LBP [10, 12, 15-17]. Additionally, literature on self-management of LBP and studies on physical activity, exercise or education (including CBT) was reviewed for inspiration for specific content for each component. Finally, patient leaflets and other patient information delivered through websites or apps were reviewed for content of self-management for LBP. The intervention mapping process for the selfBACK intervention will be described in detail in a separate publication.

3.2.1. The digital DSS

The selfBACK system constitutes a data-driven predictive DSS that uses the Case-Based Reasoning (CBR) methodology [29] to capture and reuse participant cases in order to suggest the most suitable self-management plan for participants. The data sources for the CBR system comprise 1) the initial participant data collected by the baseline web-based questionnaire, 2) a weekly report by the participant in the selfBACK app (including pain, function, fear-avoidance, workability, sleep, self-efficacy, stress, health belief and barriers), and 3) the step-detecting wearable. On a weekly basis, this information is used to revise the self-management plan by matching the characteristics of the current participant case with existing successful participant cases in the selfBACK case-base. The weekly tailoring questions will only be given if relevant for the participant. As an example, if a participant has indicated sleep problems at baseline, then a tailoring question will be asked in appropriate time-intervals, and, based on the answer, a set of educational messages on e.g. sleep hygiene will be offered to the participant. Consequently, the DSS will deliver an individualised self-management plan for the coming week via the selfBACK app. All interaction between the participant and the selfBACK DSS happens via the selfBACK app. There is no interaction between the DSS and HCPs. The architecture of the DSS and the interaction between the participant, the wearable device, the selfBACK app and the database is outlined in Figure 2. A full description of the DSS is published elsewhere [30].

[figure not shown]

Figure 2: Overview of the selfBACK decision support system.

3.2.1. Wearable device and supporting apps

The Xiaomi Mi Band 3 wristband is used to track number of steps. The step count is synchronized with the GoogleFit app on Android devices and Apple HealthKit app on iOS devices throughout the day. The wristband registers movement in all three planes (frontal, horizontal and sagittal) via an ADI (Analog Devices, Inc.) ultra-low power acceleration sensor and computes step-count from this information. It connects to the phone via Bluetooth (V4.2 BLE) and requires Android 4.4+ / iOS 9.0+.¹ The wearable device is to be worn on the participant's wrist continuously while participating in the intervention but could be taken off during sleep and water-based activities. To connect the wristband and step count function to the selfBACK app, the MiFit app is required to be installed on the participant's smartphone. Additionally, Apple HealthKit needs to be activated on iOS devices, and GoogleFit needs to be activated or downloaded if not preinstalled on Android devices. The three apps (i.e., MiFit, Apple HealthKit and GoogleFit) are freely available, and can be downloaded without cost for the participant. An account needs to be created for the apps for every participant. An installation guide has been developed to help participants install and connect apps, and a researcher will be present at the time of installation to ensure the correct setup.

3.2.2. The selfBACK self-management plans

The DSS builds the self-management plan from three types of content: 1) physical activity level (i.e., step count) and goals, 2) a bank of physical exercises, and 3) a bank of educational material. An overview of the available content is presented in Figure 3.

¹More details:

<https://www.mi.com/in/mi-band-3/specs/>

Physical activity

Physical activity is tracked as described for the wearable device (see section 3.2.1). The SELFBACK app prompts the participant to set a goal for physical activity by suggesting a gradual increase in daily steps if the past week's goal was achieved. A 10% increase is suggested, until a goal of 10.000 steps per day is reached. The participant can adjust the suggested goal, before accepting it. During the week, the participant can see the achieved step-count per day and track his/her progress. The lowest step count goal that is possible to set is 3000 steps per day. This limit is based on average step count numbers from previous studies in workplace pedometer intervention (average ~6000 steps) [31] and home-based pedometer intervention in older adults with knee problems (average ~3500 steps) [32]. The minimum step count goal of 3000 per day was chosen to reflect that participants in the trial have functional disability that may also affect their physical activity level. Based on the achieved daily step count from the previous week, the step count goal for the coming week is adjusted, and educational messages and notifications aimed to motivate more physical activity is pushed through the SELFBACK app.

Exercise programme

The physical exercise material is compiled of 70 exercises organised in 6 targets (back-, abdominal-, gluteal-, and core muscle strength, pain relief and flexibility). Each participant is given an individualised exercise programme, the default recommendation is to perform exercises in 3-5 sessions per week of 20 minutes (e.g. four exercises with an estimated duration of five min per exercise). The number of exercises is adjusted according to the participant's indication of time available for doing exercise and to the anticipated level of difficulty defined by baseline questionnaire. An exercise programme will always include either 1) a strength exercise for abdominal and back extensor muscles, or 2) one strength exercise for the core muscles. Additionally, exercises targeting strength in hip and gluteal muscles, flexibility of the spine, or pain-relieving exercises may be included in the programme. If a participant presents with an acute pain flare-up or high pain ratings, the app will offer pain-relieving exercises only until an acceptable pain level is achieved.

An exercise is presented to the participant in the app with a short video accompanied by a written instruction that includes recommendations on number of sets and repetitions. The participant will be prompted in the app to report completed number of sets and repetitions per exercise. The DSS will offer a new exercise at a more difficult or easier level in the coming week, based on the level of completion registered. In addition, participants can request new exercises (at the same level of difficulty and within the same group of exercises) if they experience problems completing the suggested exercise. The included exercises were extracted from studies identified in international guidelines for treatment of LBP [10, 33], and systematic reviews on effect of exercises in LBP treatment [34-39]. The organisation, targets and progression of exercises were guided by consensus discussions among experienced clinicians and researchers within the SELFBACK project team.

Education

The educational material is structured under 14 main categories ("information about LBP", "understanding mind-body", "self-management for LBP", "thoughts, behaviour, attitude and feeling", "fitting in self-management in a busy life", "first aid when your back hurts", "LBP and comorbidities", "goal-setting and action planning", "pacing and graded activity", "problem solving", "relaxation", "sleep and LBP", "social support" and "overcoming barriers for self-management of LBP"). For each

main category, a tree-structure of educational messages has been created. Every short message is about 140 characters long. Some messages may include links to longer, more explanatory text (max 500 characters) or tools that can be used to help with self-managing LBP, e.g. goal setting tool, sleep advice, etc. Some short messages are also rewritten into “quizzes”, where the educational content is rephrased into a yes or no type question. When answering a quiz, a response is displayed to the participant stating the correct answer with additional explanation. A total of 230 short messages or quizzes are available in the educational material.

[figure not shown]

Figure 3: Overview of available content within the selfBACK app

3.2.3. selfBACK mobile app

The individually tailored self-management plan is delivered via the selfBACK app. The selfBACK app is developed by TRX in close collaboration with the other selfBACK partners. The development of the first version of the app has been completed (by December 2017). The selfBACK app was tested in a pilot study starting August 2018 (section 7). Feedback from the pilot participants was implemented into the app; however, the core content and features did not change. The app and DSS will be frozen and tested in the RCT. To increase transparency and facilitate replicability of the intervention, the version of the app and DSS used in the RCT will be preserved. A short video representation of the app will be made publicly available after the RCT has been completed.

3.2.4. Access, frequency and mode of delivery

The participants access their self-management plan via the selfBACK app and enter data into the DSS by answering tailoring questions in the app and by wearing the connected wearable device. These data are combined with the participant self-reported outcome as outlined in Figure 2. The participant is encouraged to use the selfBACK app daily or at least once a week, in order to be offered a new self-management plan. The app will send push-notifications reminding the participant to open the app and view the new self-management plan. The participant can disable or adjust the frequency of notifications in the app settings. The goal of the intervention is that participants learn to self-manage their LBP, which may potentially result in participants discontinuing their use of the app. Consequently, discontinuation is not necessarily a sign of low compliance but may indicate a high self-management level.

3.3. Ancillary and post-trial management

All participants randomised to the selfBACK intervention can continue their use of the wearable device after the trial. However, their access to the selfBACK app will cease after the 9 months follow-up, by disabling the participants username, thereby restricting login to the app. All participants randomised to the usual care group are offered a wearable device after completing all follow-up assessments. No further post-trial management is planned.

4. Outcomes

All outcomes are collected at baseline, six weeks, three, six and nine months. Additionally, participant characteristics and demographic variables are collected at baseline. Participant characteristics include age, gender, height, weight, and relevant comorbidities. The demographic variables include family relations, ethnicity, educational status, employment, and work characteristics if employed. The outcomes included in the trial were based on recommendations for LBP trials [40-42].

4.1. Primary outcome

The RMDQ assesses pain-related disability [43]. The questionnaire includes 24 items asking participants to indicate if they experience functional impairments by answering “yes” or “no” to a series of descriptions of functional abilities [44]. The RMDQ score ranges from 0 to 24, where a higher score indicates higher levels of disability due to LBP [44, 45]. The RMDQ is a validated and recommended tool for measuring pain-related disability in LBP populations [41, 45, 46]. The minimal clinically important difference for the RMDQ has been reported to be five points in LBP populations with baseline scores ranging between 14-16 points [47]. The selfBACK trial aims to detect a two-point difference after three months. This is less than the suggested five-point reduction stated as minimally clinically important. Also, if the two-point difference does not exceed the measurement error of the RMDQ, the results will then be difficult to apply on an individual level in clinical practice. The measurement error of the RMDQ has been reported to range between 1.4-3.7 in studies comparing the RMDQ to the Oswestry Disability Index, with three studies reporting measurement error to range between 1.4 to 1.8 and one study reporting 3.7 [48]. Given that the selfBACK intervention is an add-on to usual care and supposed to be a supplement to existing treatment rather than a substitution, a smaller difference can be justified.

4.2. Secondary outcomes

The average and worst LBP intensity within the past week will be assessed by asking “Please indicate your average/worst low back pain level during the last week”, using an 11-point numerical rating scale (NRS) ranging from zero to 10. The NRS is a valid and commonly used outcome for measuring pain in adults [40, 49, 50]. Pain duration measures length of participants’ current back pain episode and total duration of time with LBP by asking “What is the length of time you have had low back pain during this episode?” with scoring ranging from less than 1 week to more than 12 weeks and “What is the total length of time that you have had low back trouble during the last 12 months?” with scoring ranging from 0 days to everyday. Measures of pain intensity and duration are recommended as a core set of outcomes for LBP trials [40]. Pain medication evaluates the frequency of non-prescription pain medication use for LBP by asking “How many days during the last week have you taken non-prescription pain medication for low back pain?”

The Fear-Avoidance Belief Questionnaire (FABQ) assesses participant’s beliefs about how physical activity and work affect their LBP [51]. The FABQ is a 5-item questionnaire, where the participants score their beliefs about their LBP on an ordinal scale ranging from zero [completely disagree] to six [completely agree]. The Pain Self-Efficacy Questionnaire (PSEQ) assesses the participant’s level of confidence in carrying out specific activities despite their pain [52, 53]. The PSEQ is a 10-item questionnaire scored on an ordinal scale ranging from zero [completely disagree] to six [completely agree].

Activity Limitation evaluates if LBP has limited work and leisure time activities. The questionnaire consists of two single items with response options “yes” and “no.” Work Ability is measured by a single-item and rated on an 11-point NRS scale ranging from zero [completely unable to work] to 10 [work ability at its best] [54].

Self-reported physical activity is evaluated by a revised version of the Saltin-Grimby Physical Activity Level Scale, where participants indicate their amount of time per week performing leisure activities with four levels of intensity ranging from sedentary to vigorous physically active [55]. Function is evaluated by the Patient Specific Functional Scale (PSFS) where the participants, on up to two self-selected activities, are asked to rate if they are unable to do or are having difficulty with their ability to perform self-selected activities regarded as important by the participants themselves [56, 57]. The ability to carry out the activity/activities is rated from zero [unable to perform] to 10 [able to perform].

Sleep is assessed by self-report using four items concerning problems with falling asleep, waking up repeatedly, waking up too early, and feeling sleepy during the day [58]. Items are scored in three categories; [seldom or never], [sometimes] or [several times a week]. The information retrieved from these four items approximates the information necessary to diagnose insomnia according to the DSM-V criteria [59]. Stress is evaluated with the Perceived Stress Scale (PSS), a 10-item questionnaire asking about frequency of thoughts and feelings related to perceived stress [60]. Participants indicate their frequency of experiencing stress-related issues on a 5-point Likert scale, ranging from [never] to [very often].

Three outcome measures are included to assess general health and perception of illness. Health-related quality of life is evaluated with the EuroQoL 5-dimension (EQ-5D) questionnaire [61]. A 5-point Likert scale ranging from [no problems] to [complete inability] is used to assess the health-related quality of life within each of the five dimensions (i.e., mobility, self-care, activities, pain/discomfort and anxiety/depression). The Brief Illness Perception Questionnaire (BIPQ) [62] evaluates the participants’ illness perception in an 8-item questionnaire. Items are scored on an ordinal scale ranging from zero [no

problems] to 10 [worst severity] [62]. The *Patient Health Questionnaire-8* (PHQ-8) is an 8-item questionnaire used to evaluate the participants' depressive symptoms [63]. Items are scored on a 4-point Likert scale scoring frequency of experiencing symptoms of depression [63]. Also, a single item question for *Patient's Global Perceived Effect* will be asked at all follow-ups, where participants are asked to rate improvement or deterioration of their LBP compared to before the intervention.

Participants randomised to the selfBACK DSS in addition to usual care are also asked a set of weekly tailoring questions used to individualise their self-management plan. The tailoring questions include items on pain (NRS for pain intensity [41]), function (item 5 from the Chronic Pain Grade Questionnaire [64]), kinesiophobia (1-item Tampa [65]), work ability (1-item WAI [54]), sleep (single item, modified from s-HUNT-Q [58]), pain self-efficacy (item 5 and 9 from PSEQ [66]), stress (4 items from PSS [60]), symptoms of depression (2 items from PHQ-8 [63]), and barriers for self-management (single item, customised to selfBACK). In total, this comprises 17 tailoring questions; however, participants will only be asked a maximum of 7 questions per week (most commonly 4 questions). The selection of the relevant questions is based on a set of rules implemented in the backend of the DSS, taking into account the progression of the self-management process and the individual participant characteristics.

5. Statistics

5.1. Sample size estimations

The study is designed as a superiority trial with two parallel groups, selfBACK in addition to usual care versus usual care only. We hypothesis that the intervention group (selfBACK in addition to usual care) will have a two-point difference in pain related disability (RMDQ) compared to the control group (usual care) at three months follow-up. The sample size calculations have been performed in two ways. First, we conducted a simple calculation assuming only one follow-up measure and a standard deviation (SD) of the RMDQ score of six points. The expected SD was informed by previous high-quality studies in DK and UK investigating similar LBP populations [67-70]. Based on these calculations we estimated that a sample size of 382 (191 in each group) was necessary to detect a two-point difference with 90% power and a two-sided alpha level of 0.05.

We then performed a simulation using 1000 repetitions of a mixed model regression for repeated measures, assuming 1) three data points per participant (i.e. baseline, six weeks and, three months), 2) an effect of treatment of two points, 3) a SD of six points, and 4) a correlation between repeated measures of 0.4. The latter was based on information from previous trials with repeated measures for the RMDQ in similar LBP populations [71, 72]. As in the simple calculations reported above, we used an alpha level of 0.05. Based on these assumptions, sample size calculations showed that 250 participants (i.e. 125 participants in each group) give a power of 92% (95% confidence interval [CI 90-93]) to detect a two-point difference in RMDQ between study groups at three months. Furthermore, simulations assuming a two-point difference between groups at both six weeks and three months indicated that a sample size of 180 (90 in each group) give a power of 94% (95% CI, 92-95). Taken together, these sample size calculations indicate that a sample size of ~250 persons (125 in each group) will be sufficient under the given assumptions if the statistical analyses utilise the repeated measure design. A recent systematic review showed that attrition rates ranged between 4-94% for digital self-management interventions lasting between two weeks and 12 months in LBP populations [25]. To allow for a 30%

drop out rate at three months follow-up we aim at including a total of 350 participants in the trial; 175 participants in each arm.

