5.2. Statistical analysis

The primary analysis will estimate the mean difference with a 95% confidence interval (CI) in RMDQ score at three months follow-up between groups (selfBACK in addition to usual care versus usual care only). The analyses will be conducted according to the intention-to-treat principle using a linear mixed model for repeated measures. This model includes all available data for all participants at each time point (i.e. baseline, six weeks, and three months). In the regression model, individual participants will be specified as a random effect, accounting for the within subject covariance structure. The effect of group and time will be specified as fixed effects using a joint variable of intervention and time. Here, baseline levels are pooled over the two study groups assuming that any baseline differences are due to chance [73]; this also controls for any baseline differences in the outcome variable. The analysis will investigate the effect of the intervention as constant over time, as well as an interaction between time and group allocation. The between group difference will be estimated both in a crude model, and adjusted for the two variables used for stratification in the randomisation i.e. country and care provider [74]. Further adjustment for baseline levels of other prognostic factors will be considered.

Any missing values are inherently accounted for in the mixed model approach [75], but multiple imputation methods and complete case analysis will be applied in sensitivity analyses. Possible modifiers of the effect of intervention on the primary outcome will be assessed in supplementary analyses stratified by gender, age groups, socioeconomic status and different levels of LBP severity etc., and accompanied by tests of statistical interaction.

Secondary outcomes will be analysed using a similar approach as described above for the primary outcome, with linear mixed models for repeated measures. Analyses of data from six- and nine-months follow-up will also be analysed according to the above description for the primary outcome. The precision of the estimates from the statistical analyses will be assessed by 95% CI.

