#### Sample size

Based on sample size and drop-out calculations (power of 90% to detect a 2-point mean group difference in RMDQ score at 3 months and a 30% drop-out rate during follow-up), the main trial aimed for 350 participants but included as many as 461 participants (ref protocol and main), with 300 of these participants from Denmark eligible for this analysis. The SELFBACK trial was powered for the clinical outcome but not the cost-effectiveness analysis.

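### Protocol 5.1 power of 92% (n=250) and 94% (n=180) does not follow from SD 6, correlation 0.4 and two-sided 0.05, which give about 82% and 86%

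*Protocol*

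**What the plan says.** Protocol 5.1 (Sample size estimations) states the hypothesis that the intervention group "will have a two-point difference in pain related disability (RMDQ) compared to the control group (usual care) at three months follow-up". It sizes the trial in two ways.

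- **Simple calculation**, "assuming only one follow-up measure and a standard deviation (SD) of the RMDQ score of six points": 382 participants (191 per group) for 90% power at two-sided alpha 0.05.
- **Simulation**, 1000 repetitions of a repeated-measures mixed model with three time points, a two-point effect, SD 6, correlation 0.4 and alpha 0.05 as in the simple calculation. For the three-month difference: "250 participants (i.e. 125 participants in each group) give a power of 92% (95% confidence interval [CI 90-93"). For a two-point difference at both six weeks and three months: "a sample size of 180 (90 in each group) give a power of 94% (95% CI, 92-95").

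From this, 5.1 concludes that about 250 suffice and sets 350 to allow for 30% drop-out.

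Protocol 5.2 (Statistical analysis) specifies a random participant effect and a primary estimate at three months, and says that "baseline levels are pooled over the two study groups assuming that any baseline differences are due to chance". It adds: "The analysis will investigate the effect of the intervention as constant over time, as well as an interaction between time and group allocation".

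The cost-effectiveness SAP (Sample size) summarises the main trial's basis as "power of 90% to detect a 2-point mean group difference in RMDQ score at 3 months and a 30% drop-out rate during follow-up", and records that "the main trial aimed for 350 participants but included as many as 461 participants".

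**The concern.** The simulated powers carry the whole reduction from 382 to about 250, and hence the target of 350. Using a baseline and a six-week measure that correlate at only 0.4 with the three-month score removes 16% of the variance of the three-month contrast (1 − 0.4² = 0.84). A 16% reduction applied to 382 leaves about 321, not 250. So the printed figures look too favourable for the printed inputs.

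If they are wrong, the chance of missing a true two-point difference at three months, at the planned size and drop-out, is nearly twice the 10% that the SAP's statement implies. Anyone reusing SD 6 and correlation 0.4 with these powers would also under-size a new trial.

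**Working it through.** **Inputs.** From Protocol 5.1: difference 2, SD 6, correlation r = 0.4, alpha 0.05 (two-sided, by reference back to the simple calculation), 1000 repetitions. From 2.6: 1:1 allocation. From 5.2: random participant effect and pooled baseline. Section 5.1 does not state the covariance structure or baseline handling of the simulation. I infer exchangeable correlation and pooled baseline from the 5.2 model.

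**Simple calculation.** n per arm = 2 × 36 × (1.960 + 1.282)² / 2² = 189.1, so 190 by the normal approximation and 191 by the t-test. The printed 382 reproduces, so SD 6 and two-sided 0.05 behave as stated there.

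**General form for the mixed model.** SE = sqrt(2 × 36 × f / n per arm); power = Φ(2/SE − 1.960). The factor f depends on the parameter tested.

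1. *Three-month contrast, six-week effect free:* f = 1 − r² = 0.84. At 125 per arm, SE = sqrt(72 × 0.84/125) = 0.6956, 2/SE = 2.875, **power 82.0%**.
2. *Three-month effect with the six-week effect fixed at zero:* f = 0.771. At 125 per arm, SE = 0.667, 2/SE = 3.000, **power 85.1%**.
3. *Constant effect at both follow-ups:* f = (1 + r)/2 − r² = 0.54. At 90 per arm, SE = 0.657, 2/SE = 3.043, **power 86.1%**.

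Simulations of the same model (4000 repetitions) gave 81 to 83% for case 1 and 86 to 87% for case 3.

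**Distance from the printed figures.**

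| Scenario | Printed (95% CI) | Recomputed | Gap in Monte Carlo SE |
|---|---|---|---|
| n=250, three months | 92% (90-93) | 82.0% | 0.10 / sqrt(0.82 × 0.18/1000) = 8.2 |
| n=180, both follow-ups | 94% (92-95) | 86.1% | 0.079 / sqrt(0.861 × 0.139/1000) = 7.2 |

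**Other two-sided readings at 125 per arm.**

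| Reading | Power |
|---|---|
| Linear divergence | 83.8% |
| Follow-up only, no baseline | 75.0% |
| Baseline not pooled | 67.2% |
| Constant effect | 94.8% |

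None falls in 90-93. Correlation that decays over time (AR(1), 0.4 between adjacent visits) widens the gap: 76% and 81% for the two printed scenarios.

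**Planned and actual size, three-month contrast.**

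- 350 with 30% loss leaves 245, or 122.5 per arm: 81.2%. If every drop-out still supplies six-week data: 82.2%. With the six-week effect fixed at zero: 84.4%.
- The same 122.5 per arm under a constant effect: 94.4%.
- 461 with 30% loss leaves about 322, or 161 per arm: 90.4%.

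**What would reproduce the printed figures.**

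- *Higher correlation:* 0.622 gives 92% at 125 per arm and 0.647 gives 94% at 90 per arm. Values of 0.60 to 0.64 fall inside both printed intervals.
- *Smaller SD, with r = 0.4:* 5.13 and 5.20 match the point figures; about 5.1 to 5.3 fits both intervals. At SD 5.15, however, the simple calculation would need about 140 per arm (280 in total), not 382.
- *One-sided test:* 89.1% at 125 per arm (91.2% with the six-week effect fixed at zero) and 91.9% at 90 per arm.

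**The case against.** The strongest counter-argument is sidedness. The protocol writes two-sided only for the simple calculation. A one-sided test with the six-week effect fixed at zero gives 91.2% for n=250, inside the printed interval, and 91.9% for n=180, just below its interval. Allowing for rounding and Monte Carlo error, that is close to both figures with SD 6 and r = 0.4 intact. This stands as a possible cause. It does not defend the text, because the simulation's alpha is tied to the simple calculation, which was two-sided.

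Second, 82% rests on an inferred parameterisation; 85% (84% for 350 with 30% loss) is the most favourable two-sided value for a three-month effect under exchangeable correlation. That is fair, but the upper value is still well below 90%. Section 5.2 names the three-month difference as primary and uses joint intervention-by-time terms, which points to 82%.

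Third, a constant effect is one of the two forms named in 5.2 and gives 94.4% at 245. This is correct, but neither 5.1 (for the 92%) nor the SAP gives that as the basis.

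Fourth, the SAP concerns cost-effectiveness and only summarises the main trial's target, and the main trial's own SAP is not among the documents. It might explain the simulation. Finally, 461 were included, which restores about 90% power. That limits the consequence but does not make the printed figures right.

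**Conclusion.** The concern holds. On the printed inputs, the two simulated powers are overstated by about 10 and 8 percentage points. The SAP's 90% for 350 with 30% drop-out is not met for the three-month contrast (81 to 82%), but is met for a constant two-point effect (94.4%). This rests on two-sided 0.05, exchangeable correlation 0.4 and pooled baseline. No two-sided variant tried with SD 6 and correlation 0.4 gives both printed powers. The documents do not show whether an input or an output is misprinted.

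The practical effect is confined to the sample-size justification. Planned power stays above 80%, the enrolled 461 give about 90% at 30% loss, and no analysis or conclusion changes.

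**What to change.** Check the simulation code, then do one of the following.

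- **(a) Another correlation, SD, sidedness or parameterisation was used.** Print it and justify it. A correlation of 0.60 to 0.64 would give 90 to 92% for 350 with 30% loss. An SD of about 5.1 to 5.3 would also fit, but the simple calculation of 382 would then have to be revised too.
- **(b) SD 6, correlation 0.4 and two-sided 0.05 stand.** Restate the power as 82% (n=250, three-month contrast), 86% (n=180, constant effect) and 81 to 82% (350 with 30% loss, three-month contrast; 94% or more if the effect is constant). Amend the 90% in the SAP's Sample size section to say which contrast it refers to.

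In both cases, state the covariance structure, the tested parameter and the baseline handling of the simulation. If the code fixed the six-week effect at zero, say so and report the figures for that model (85% for n=250, 84% for 350 with 30% loss).

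The cost is a code check and wording. Under (b) the stated power for the primary contrast becomes less favourable. No change to enrolment or analysis is needed.
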